5. SUBJECT ENROLLMENT

Before subjects may be entered into the study, REMD Biotherapeutics, Inc. requires a copy of the site's written IRB approval of the protocol, informed consent form (ICF), and all other subject information and/or recruitment material, if applicable. A subject is considered enrolled once the subject is randomized. However, if a subject has been randomized and does not receive study drug, the subject may be replaced. All subjects must personally sign and date the informed consent form, before any study specific procedures are performed.

All subjects who enter into the screening period for the study (defined as the point at which the subject signs the informed consent) will receive a unique subject identification number before any study procedures are performed. This number will be used to identify the subject throughout the clinical study and must be used on all study documentation related to that subject. The subject identification number must remain constant throughout the entire clinical study; it must not be changed at the time of rescreening, enrollment, or randomization. This number will not be the same as the randomization number assigned for the study. Screening procedures/tests may be repeated and reevaluated per Investigator discretion and sponsor approval.

The unique study identification number will consist of 7 digits. The first 3 digits will represent the last 3 digits of the protocol number (e.g., 202). The 4th digit will be an alphabet representing the site code (i.e., site number for the first center is A, site number for the second center is B) and will be identical for all subjects at the same site. The next 3 digits will be assigned in sequential order as subjects are screened (e.g., 001, 002, 003). For example, the first subject to enter screening at site A will receive the number 202A001, and the second subject at the same site will be 202A002.

Treatment Assignment

Subject eligibility will be established at the conclusion of the baseline evaluations, and subjects will then be randomized in a double-blind fashion. The proposed dose design for the current study is for subjects to be randomized in a 1:1:1 fashion into one of three treatment groups (placebo, 35 mg REMD-477, or 70 mg REMD-477).

Enrollment will take place at 7 to 8 centers in North America. A blinded central randomizer identified by REMD Biotherapeutics will be used to assign the randomization number for all subjects randomized into this study. The unblinded pharmacist or designee at each of the

sites will prepare study drug according to the randomization schedule.

Randomization

Randomization to placebo, 35 mg REMD-477, or 70 mg REMD-477 will be based on a randomization schedule prepared by the CRO's designated unblinded biostatistician and provided to each of the unblinded site pharmacist or designee before the start of the study.

Subjects will be considered randomized once a unique subject randomization number has been assigned. Randomization of a subject may occur within a day prior to Day 1, after subject's eligibility has been confirmed.

After subjects have completed the screening procedures and are confirmed to be eligible for the study, they will be assigned a 5-digit randomization number based in the sequential order in which they met eligibility. The 5-digit randomization number will follow the convention SRXXX, where S is the site code (A, B, C, D, E, F, G, or H), R is a replacement number (with the initial subject to be marked as "0"), and XXX is a sequential randomization number from 001 to 075 for Part A of the Protocol, and 101 to 175 for Part B of the Protocol.

In the event subjects are randomized, but are withdrawn before receiving study medication, a replacement subject may be enrolled in the subject's place and assigned to receive the identical treatment as the replaced subject. The replacement subject will receive a randomization number that is identical to the replaced subject, except that the number '1' will be added to replace "0" in the thousands place of the 5-digit randomization number (e.g., subject A₁001 replaces subject A₀001).

6. TREATMENT PROCEDURES

Investigational Product Dosage, Administration, and Schedule

REMD-477 will be manufactured and packaged by a certified contract manufacturing organization (CMO) and distributed using GCP-compliant clinical trial drug distribution procedures. REMD-477 is supplied as single-use glass vials. REMD-477 is formulated with 10mM sodium acetate, pH 5.2, 5% (w/v) sorbitol, 0.004% polysorbate 20 at a protein concentration of 70 mg/mL.

The formulation of placebo is 10 mM sodium acetate, pH 5.2, 5% (w/v) sorbitol, 0.004% polysorbate 20. REMD-477 or vehicle is to be administered SC using 1 mL size insulin syringes.

Approximately 150 subjects (75 in Part A and 75 in Part B) will be randomized in a 1:1:1 fashion into one of three treatment groups (placebo, 35 mg REMD-477, or 70 mg REMD-477).

SC doses of placebo, 35 mg REMD-477, or 70 mg REMD-477 will be administered at the CRU by a qualified staff member on Day 1, followed with repeated weekly doses for an additional 11 weeks. Twelve total weekly SC doses of placebo, 35 mg REMD-477, or 70 mg REMD-477 will be administered at the CRU by a qualified staff member on Days 1, 8, 15, 22, 29, 36, 43, 50, 57, 64, 71, and 78. Each subject will receive his/her study drug SC injections at the same time of the day as administered on Day 1 (+/- 1 hour).

Each dose will be divided into two blinded 0.5 mL volume SC injections administered to the subject's anterior abdominal wall, for a total dose volume of 1 mL. For the 70 mg REMD-477 dose group, subjects will receive two 0.5 mL SC injections of 70 mg/mL REMD-477 on each scheduled day of dosing. For the 35 mg REMD-477 dose group, subjects will receive one 0.5 mL SC injection of 70 mg/mL REMD-477 and one 0.5 mL SC injection of placebo on each scheduled day of dosing. For the placebo dose group, subjects will receive two 0.5 mL SC injections of placebo on each scheduled day of dosing. For each scheduled dose, the two 0.5 mL SC injections should be placed at a distance of 2 cm apart. Alternating (left or right) sites on the subject's anterior abdominal wall and at a distance of at least 2 cm apart will be used for subsequent SC dosing.

The Principal Investigator or a designee must be present during administration.

Documentation of the investigational product or matching placebo administration will be

noted on the electronic case report form (eCRF) page and in the source documents. The date, dosage and time of administration for dose will be recorded on the respective eCRF page.

The effects of overdose of REMD-477 are not known. All overdose occurrences must be documented, and corresponding AEs recorded on the appropriate eCRF page and in source documents.

The Pharmacy Guide is provided in [Appendix B](#). Details in preparing and administering all study products are included in the Pharmacy Binder provided by REMD Biotherapeutics prior to the start of the study.

Other Protocol-Required Drugs

There are no other protocol-required drugs.

Safety Data Review and Stopping Rules

Safety Review Committee

The Safety Review Committee meeting will be held via teleconference to review available study data and monitor subject safety. The Safety Review Committee will be composed of the Investigator(s) and REMD Biotherapeutics Medical Monitor and Clinical Operations Director. Additional members may be added as needed. The Committee may recommend to continue dosing, to delay dosing, to increase enrollment, to disqualify a subject, or to decrease/increase dose based on emerging safety, PK, and PD data from this current study or the completed phase 1b/2a study (Protocol R477-201) in type 2 diabetic subjects. Final decisions will be determined by the ~9 -12 voting Safety Review Committee members who include the REMD Biotherapeutics medical monitor and clinical operations director, and the 7- 8 Investigators. At least three fourths of the voting Safety Review Committee members must agree to the decision. All available study data including demographics, medical history, concomitant medications, adverse events, ECG, vital signs, and laboratory results will be reviewed. Data to be reviewed may not necessarily be validated and cleaned (data query resolution may be pending).

Data will be reviewed blinded (i.e., treatment assignment will not be revealed) unless unblinding is deemed necessary for the Safety Review Committee. If deemed necessary, unblinding will be performed according to REMD Biotherapeutics standard procedures.

Safety Data Review

Study recruitment, progress and safety issues will be reviewed by the investigators, research nurse and research coordinators and communicated to the sponsor on a regular basis. The following will be reviewed: 1) subject enrollment, 2) preliminary findings that might affect the risk/benefit ratio or alter the procedures described in the protocol, 3) any clinically-significant out-of-range laboratory value and a course of action, and 4) any adverse or serious adverse events that might result from the research procedures.

The Safety Review Committee will review all available safety and PD data periodically during the study when approximately 33%, 66%, and 100% of the subjects in Part A have received a randomized treatment. After each safety data review, the Safety Review Committee will decide whether or not to continue with subject enrollment and dosing. Decisions to continue enrollment will be documented in the Safety Review Memo. REMD Biotherapeutics will issue a written notification of these decisions to investigators.

Determination of Adverse Event Severity and Relatedness

Adverse events will be coded per current MedDRA. Determination of the severity of adverse events will be consistent with Common Terminology Criteria for Adverse Events (CTCAE) V. 4.03. The relationship of an adverse event to treatment will be determined by the Investigator (see section 9: Reporting Procedures for All Adverse Events).

Dose Stopping Rules

Dosing will be stopped or modified if treatment-related AEs, changes in vital signs, ECG, or clinical laboratory results are observed and these changes pose a significant health risk, in the opinion of the Sponsor, Principal Investigator or Medical Monitor.

Medically significant AEs considered to be related to the investigational product and serious adverse events considered to be related to study procedures will be followed until resolved or considered stable.

A subject may be terminated at any point in time at the discretion of the Sponsor, Principal Investigator or Medical Monitor.

Stopping Rules for an Individual Subject:

At any time during the study, the subject must discontinue study drug treatment, if one of the following events occur:

- An increase of AST and/or ALT (> 3x ULN) are observed in the presence of increased (> 2x ULN) alkaline phosphatase and/or total bilirubin.
- A sustained AST or ALT increase, defined as three consecutive values of AST and/or ALT greater than 5x ULN within a period of 14 days.
- A treatment-related Grade 3 or greater adverse event (other than AST or ALT increase as described above) is noted by the Investigator.

If any of the above stopping rules are met the following action(s) should be taken:

1. Stop dosing and convene a Safety Review Committee meeting;
2. Review AE for evidence of relationship to treatment;
3. Consider unblinding, as appropriate*;
4. May resume enrollment and continue the study if recommended by the Safety Review Committee.

**A subject's treatment assignment should only be unblinded when knowledge of the treatment is essential for the further management of the subject, or may impact the safety of subjects currently enrolled.*

Concomitant Therapy

Throughout the study, the Principal Investigator may prescribe concomitant medications or treatments deemed necessary to provide adequate medical care.

For subjects enrolled in this study, the allowable concomitant medications include insulin, angiotensin converting enzyme inhibitors, angiotensin receptor blockers, beta adrenergic receptor blockers, calcium channel blockers, diuretics, HMG-CoA reductase inhibitors, fibrates, low-dose aspirin, NSAIDs, and hormone replacement therapies (estrogen or thyroid). Subjects on an SGLT2 inhibitor should discontinue the SGLT2 inhibitor during the Screening period, at least 2 weeks prior to the start of the Lead-in Period. The use of any other concomitant medication requires Investigator's discretion and must not interfere with the study outcomes. Doses of allowable concomitant medications must be stable for > 1 month prior to Day 1.

Any use of concomitant therapy or treatments will be recorded in the applicable eCRF page with appropriate source documentation.

Proscribed Therapy during Study Period

Current or recent (within 1 month of screening) use of diabetes medications other than insulin, or use of other medications that are known to affect the outcome measures are prohibited for this study.

No other medication (with the exception of those listed above) is to be taken within 2 weeks or 5 half-lives (whichever time period is greater) before Day 1 and through the duration of the study. All herbal or nutritional supplements are subject to investigator's discretion.

Any concomitant medication used to treat a medical emergency or as rescue medication for hyperglycemia will be subject to investigator's review and endorsement for continuation in the study, and will be documented on the appropriate eCRF page and in the source documentation.

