This two part study (Parts A and B) will be conducted at multiple sites in the United States. In each part, approximately 75 subjects (150 subjects in total across Parts A and B) with Type 1 diabetes on stable doses of insulin will be randomized in a 1:1:1 fashion into one of three treatment groups (placebo, 35 mg REMD-477, or 70 mg REMD-477). The enrollment of Part B may be initiated prior to the completion of Part A. Subjects will receive once weekly SC injections of investigational product for 12 weeks and be followed for an additional 12 weeks during washout in the Safety Follow-up Period. At baseline, throughout the treatment period, and during the 12-week Safety Follow-up Period, subjects will be evaluated for measures of glycemic control, daily insulin requirements, and safety. For subjects enrolled in Parts A and B, CGM and seven-point glucose profile will be conducted to assess the effect of REMD-477 versus placebo on glucose variability and metabolic control. For a subset of subjects in Part A who were enrolled prior to Protocol Amendment #1, beta cell function after mixed meal and arginine challenge will be examined. For subjects in Part A, alpha cell function will be assessed by measuring fasting glucagon, active and total glucagon-like peptide 1 (GLP-1), and glucagon and GLP-1 (active and total) AUC after the MMTT.

For a subset of subjects in Part A who were enrolled prior to Protocol Amendment #1, eligible subjects will be admitted to the clinical research unit (CRU) on the evening of the Baseline Overnight Visit (which can occur between Study Day -8 to Day -2), the Week 13 Visit (admission

Day 84), and the Week 24 Visit (admission Day 161). For ongoing subjects at the time of the Protocol Amendment #1, the overnight admissions to the CRU at Baseline, Week 13 and Week 24 will not occur.

For a subset of subjects in Part B, the magnetic resonance imaging – proton density fat fraction (MRI-PDFF) and FibroScan® (where feasible) will be performed prior to dosing on Day 1 (or up to 7 days prior to the Day 1 visit, after all other inclusion and exclusion criteria have been met) and on Day 85 (+/- 2 days) of Week 13.

Primary, Secondary, and Exploratory Endpoints:

Primary Endpoints:

- Change from baseline at Week 12 in daily insulin use.

Secondary Endpoints:

- Change from baseline at Week 13 in fasting glucose and glucose AUC after the MMTT – in Part A only.

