Seven-point blood glucose profiles (measuring glucose via finger stick, at the following times of day: before each meal, 2 hours after each meal, and at bedtime) will be performed for periods of three consecutive days. During the **Lead-In Period**, subjects will record their seven-point blood glucose (BG) profile over a period of three consecutive days either, prior to the Baseline Visit (subjects participating in Part A), or prior to the Day 1 Visit (subjects participating in Part B). During the **12 week Dosing Period** and **12 week Follow-up Period**, seven-point BG profiles will be performed over the three consecutive days following Dose 4 (Study Days 23 – 25), Dose 8 (Study Days 51 – 53), and Dose 12 (Study Days 79 – 81), and during Weeks 16 and 20 of the Follow-up Period.

Subjects will be provided with a blood ketone meter and blood ketone test strips in order to

measure blood ketone readings via finger-stick method. For subjects in Part A only, blood ketone readings will be performed in the morning and collected by the subject while in a fasted state, prior to the subject's morning meal. During the 12-Week Dosing Period (starting on Day 1 and continuing through the completion of Week 12) the blood ketone readings will be performed 3 days a week – on an alternate day basis starting on Day 1 (e.g. Week 1: Study Days 1, 3, 5 or on Mondays, Wednesday, and Fridays), and once weekly during the 12-Week Follow-up Period. Subjects will be instructed to contact the investigator if they have positive ketones and blood sugars > 300mg/dL. Subjects enrolled in Part B will also be provided with a blood ketone meter and blood ketone test strips to be used as needed, however, there is no required collection schedule. Subjects in Part B will be advised to perform blood ketone readings via finger-stick method when they feel ill, or symptomatic of ketoacidosis, or as instructed by the investigator.

The Type 1 – Diabetes Distress Scale (T1-DDS) and WHO-5 Well-Being Index scales ([Appendix D](#)) will be provided to the subject at the beginning of the following study visits: OBV and Day 85 and Day 161(EOS) visits.

PK blood samples and fasting plasma glucose samples will be collected as described in the Schedule of Assessments. For those samples that are scheduled for collection on days when study drug is administered, those samples should be collected pre-dose.

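### No scheduled Safety Review Committee review is triggered by Part B, so Part B data are reviewed on schedule only if they already exist at a Part A trigger

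*Protocol*

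**What the plan says.** Protocol Section 6 (Safety Data Review) sets the committee's calendar by Part A alone: reviews fall when about "33%, 66%, and 100% of the subjects in Part A have received a randomized treatment". The consequence of each is explicit: "After each safety data review, the Safety Review Committee will decide whether or not to continue with subject enrollment and dosing". The decision is recorded in a Safety Review Memo.

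The data reviewed are not limited by part. The same section says "The Safety Review Committee will review all available safety and PD data periodically during the study", and the committee description adds "All available study data including demographics, medical history, concomitant medications, adverse events, ECG, vital signs, and laboratory results will be reviewed".

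On size, Section 6 states "Approximately 150 subjects (75 in Part A and 75 in Part B) will be randomized in a 1:1:1 fashion into one of three treatment groups". On timing, the Synopsis and Section 3 both say "The enrollment of Part B may be initiated prior to the completion of Part A", without giving the extent of any overlap.

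Outside the calendar, Section 6 lists individual stopping rules that apply at any time in the study. The first action when one is met is "Stop dosing and convene a Safety Review Committee meeting". Site staff also review safety regularly and report to the sponsor.

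**The concern.** Part B gives the same two active doses, weekly for 12 weeks, to as many subjects as Part A. The committee's recurring decision to continue is nevertheless tied only to Part A accrual. A Part B subject first dosed after the last Part A trigger is treated with no scheduled continuation decision ahead.

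What is at stake is recognition of a pattern across subjects. Protocol Section 2 reports ALT rises up to 3x ULN in 7 of 12 subjects in the 70 mg cohort of the type 2 study, plus one isolated value of 18x ULN. It also expects 10- to 30-fold accumulation with weekly dosing (Dose Selection Rationale), so effects may appear well after the first dose that sets the trigger. Part B is the only part that collects the liver-injury biomarkers, but no committee review is timed to look at them. CGM in Part B is hidden from subject and investigator. For finger-stick ketones the Part B text says "however, there is no required collection schedule", although serum ketones are still drawn at baseline and at every weekly dosing visit.

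**Working it through.** **1. Where the scheduled reviews fall.** Inputs: 75 subjects in Part A, 150 in total, fractions 33%, 66% and 100% (Section 6).

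| Trigger | Part A subjects dosed | Share of planned 150 |
|---|---|---|
| 33% | 0.33 × 75 = 24.75, about 25 | 24.75/150 = 16.5% |
| 66% | 0.66 × 75 = 49.5, about 50 | 49.5/150 = 33% |
| 100% | 75 | 75/150 = 50% |

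The trigger is receipt of treatment, so at the third review the last Part A subject may have had 1 of 12 doses.

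**2. Part B subjects reached by the schedule.** Let k be the number of Part B subjects already dosed at the third review. Then 75 − k are first dosed with no scheduled review to come. Under 1:1:1 allocation, about two thirds of these are on active drug. The documents do not give k, so these values are assumptions:

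| k | No scheduled review: 75 − k | Of these on active: (75 − k) × 2/3 |
|---|---|---|
| 0 | 75 | 50 |
| 25 | 50 | about 33 |
| 50 | 25 | about 17 |

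The k subjects who are reached contribute only the data they have by then.

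**3. Would the event-driven meeting pick up the reported ALT pattern?** Section 2 describes rises up to 3x ULN, one isolated 18x value that fell below ULN with continued dosing, and no associated bilirubin or alkaline phosphatase increase. Against the three individual rules in Section 6:

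- *AST/ALT above 3x ULN with alkaline phosphatase and/or bilirubin above 2x ULN.* Not met, because there was no accompanying rise.
- *Three consecutive values above 5x ULN within 14 days.* Not met by rises up to 3x or by one isolated value. Scheduled on-treatment chemistry in Part B falls on Days 8, 15, 29, 43, 57 and 85 (Appendix A). The closest three draws, Days 8, 15 and 29, span 21 days, or 19 with the ±1-day windows (Day 9 to Day 28). The rule can therefore be met only with unscheduled draws.
- *Treatment-related Grade 3 or higher event.* The rule carves out AST or ALT increases described in the two rules above. Read broadly, it excludes all transaminase rises. Read narrowly, a single very high value might still count. On either reading it assesses one subject at a time.

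No rule counts subjects, so several isolated rises would not convene the committee.

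**4. Other looks at the data.** The unblinded preliminary analysis (Protocol Section 10, SAP Section 11) is optional, serves business and planning purposes, and follows the 30th and 60th subjects to complete Day 85. Both could be Part A subjects. SAP Section 10.4.2 tabulates ALT above 3x, 5x and 10x ULN by treatment, but does not schedule those tables for the committee.

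**The case against.** A reader might infer that half the trial lies outside the scheduled safety review. The documents do not support that. The reviews cover all available data and Part B may start before Part A is complete, so Part B data present at a Part A trigger fall within that review.

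Nor is the committee absent from Part B otherwise. A stopping-rule event in any subject convenes it. Its voting members include the investigators, the medical monitor and the clinical operations director, who already see safety information as it arises. Laboratory results are reviewed before each dose, serious events are reported within 24 hours, and the sponsor, investigator or medical monitor can stop or modify dosing.

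Part B monitoring is not simply thinner either. Only the finger-stick ketone schedule is dropped. Seven-point glucose profiles continue, liver-injury biomarkers are drawn at five timepoints, and sites with FibroScan may scan a subset, with a further scan at the first AST or ALT above 3x ULN. The type 2 cohort with 7 of 12 ALT rises included 3 placebo subjects. The Part A wording may also be deliberate, since the doses are the same; no rationale is given.

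All of this stands, and it limits the point to the absence of a guaranteed review. It does not supply a scheduled cumulative look, with a recorded decision, at Part B data that arrive after the last Part A trigger.

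**Conclusion.** The concern holds in limited form. None of the three scheduled reviews is triggered by Part B, and all three are over once 75 Part A subjects have had a first dose. Between 0 and 75 Part B subjects could be first dosed after that point; the number depends on an overlap the documents do not state. For those subjects the committee is required to meet only if an individual stopping rule is met, and the transaminase pattern in Section 2, as a cluster, would not meet one.

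This rests on reading the trigger as first receipt of treatment and on finding no Part B trigger in either document. It is not a finding that Part B lacks safety oversight. The chance that an event of some assumed rate occurs among Part B subjects would not measure the gap, because that chance is the same whatever the review calendar.

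**What to change.** Amend Protocol Section 6 (Safety Data Review) so that the committee also reviews cumulative Part A and Part B data when approximately 33%, 66% and 100% of Part B subjects have received a randomized treatment. That is about 25, 50 and 75 Part B subjects. Each review should end in the same continuation decision and Safety Review Memo. No dose or stopping rule changes.

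The cost is protocol wording and up to three further teleconferences of the existing committee. If the Part A wording was deliberate, the protocol should say so and state when the committee will review Part B data.
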